##### 4.5.6.2. SARS-CoV-2 Infection Results via Nucleocapsid Protein Testing

Nucleocapsid protein IgG results will be listed. The results will support a sensitivity analysis of the primary immunogenicity endpoint excluding subjects with an increase in nucleocapsid protein IgG levels potentially indicative of a natural SARS-CoV-2 infection prior to the immunogenicity testing visit.

##### 4.5.6.3. Physical Examinations

The performance of physical examinations will be listed. Findings upon physical examination at screening will be added to the Medical History case report form if they started prior to the signing of the ICF, and to the AE case report form page if starting afterward.

## 4.6. Other Analyses

### 4.6.1. Disposition

All subjects screened will be accounted for in disposition summaries. A summary table will be presented specifying the number of subjects who were screened, were vaccinated, completed the active trial phase, completed the trial, completed each FU visit, and are included in each analysis set. Subjects who discontinued will also be summarized by reason for discontinuation from the active trial phase and/or the trial. Subjects who completed or discontinued early during the Active Trial Phase but completed all FU visits will be considered as having completed the trial.

A listing will be presented for all vaccinated subjects by trial part and cohort.

### 4.6.2. Analysis Populations

Frequencies and percentages of each analysis population will be presented by vaccination arm (for part A) and by cohort. All subjects who signed ICF but are not eligible for the trial will be listed, including the reason for ineligibility. Reasons for exclusion from the IAS will be presented in a table.

### 4.6.3. Protocol Deviations

A protocol deviation is any noncompliance with the clinical trial protocol. The non-compliance may be either on the part of the subject, the investigator, or the trial site staff. Protocol deviations are collected on both the site level and the subject level. Subject-level deviations will be databased and listed. Categorized deviations will be presented using frequencies and percentages for the Safety Analysis Set.

### 4.6.4. Demographics and Baseline Characteristics

Tables of descriptive statistics for demographics will be produced for the Safety Analysis Set and the IAS. Descriptive statistics will be presented for the continuous demographic variables. Categorical demographic and baseline variables will be summarized using frequencies and percentages. The following demographic variables will be presented.

#### Demographic Variables

- Age at Informed Consent (years)
- Age Group (18 to <65 years, ≥ 65 years)
- Sex (Male, Female)
- Race (White, Black or African American, Asian, Native Hawaiian or Other Pacific Islander, American Indian or Alaska Native, Multiple, Not Reported)
- Ethnicity (Hispanic or Latino, Not Hispanic or Latino)
- BMI [kg/m^2]
- Prior vaccination regimen
  - Cohort 1:
    - 2 doses of mRNA vaccine,

- 1 dose or 2 doses of adenovirus-based vaccine,
- 1 dose of adenovirus-based vaccine followed within 3 months by 1 dose of mRNA vaccine,
- Other authorized primary vaccination regimen.
- Cohort 2:
  - 2 doses of mRNA primary vaccines plus 1 booster dose of mRNA vaccine,
  - 1 dose or 2 doses of adenovirus-based primary vaccines plus 1 booster dose of mRNA vaccine,
  - Other authorized primary vaccination and boost vaccination combinations.
- Baseline Neutralizing Antibody Result (< LLOQ, ≥ LLOQ to < median, ≥ median)
  - Median is calculated from the corresponding trial part and cohort values ≥ LLOQ
- Time from Previous Vaccination (time from the most recent COVID-19 vaccination to the trial vaccination)
  - Time is calculated in months as (date of trial vaccination – date of most recent vaccination + 1)/30.4375
- History of SARS-CoV-2 Infection (Yes vs. No)
- Baseline Comorbidity (Yes vs. No, see Section 4.1.6)

#### 4.6.5. Prior and Concomitant Medications

Displays of **prior** medications include medications where end date is before date of administration of trial vaccine. Displays of **concomitant** medications include all ongoing medications, medications with missing end dates, or medications with end date after administration of trial vaccination. Tables by ATC Level 2 class and preferred name will be presented for the Safety Analysis Set. If ATC Level 2 class is not available, the next highest class available will be used. Subject level listings will be created by trial part, cohort, vaccination received (Part A only) subject, ATC Level 2 class, preferred name, verbatim term, medication start and end dates, and medication ongoing status.

#### 4.6.6. Medical History and Baseline Signs and Symptoms

Medical history data are collected at screening and include conditions that started prior to signing of the ICF. Baseline signs and symptoms are adverse events that occurred between signing of the ICF through the time just prior to trial vaccination. These data are coded according to MedDRA similarly to AEs. Medical history events and baseline signs and symptoms combined will be summarized by trial part, cohort, and vaccination arm (Part A only) within SOC and PT for the Safety Analysis Set to give a full accounting of pre-vaccination prevalence of events in the trial population. SOCs and PTs within SOCs will be sorted by descending frequency in the overall column for Cohorts 1+2 combined.

Separate subject level listings will be generated for Medical History and Baseline Signs and Symptoms as they were collected separately.

#### **4.6.7. Prior COVID-19 Vaccination and History**

Prior vaccination for SARS-CoV-2 was recorded at baseline and will be reported separately from prior medications, but in the same fashion as prior medications.

Prior COVID-19 infection and prior hospitalization for COVID-19 infection will be included as a baseline COVID-19 related characteristic. Individual infection events and associated hospitalizations will be included in a listing, including the start and end date of the events.

For Part A subjects, prior COVID-19 vaccination regimen was a randomization stratification factor. The subgroup analysis for the primary objective by prior vaccination will be performed both as randomized as well as by the derived prior vaccination regimen from the COVID-19 vaccination data.

#### **4.6.8. Time to COVID-19 Infection**

Time to COVID-19 infection in days will be summarized within trial part for each cohort and vaccination arm (for Part A only) using the safety analysis set as an exploratory safety analysis. PCR results and AE data will be used to determine the occurrence of COVID-19 infection for each subject, as well as the date of COVID-19 infection. Subjects with multiple infections during the trial will be analyzed using their earliest detected infection. Subjects who do not have a positive COVID-19 result will be censored at the date of the last visit attended prior to the analysis.

The date of earliest detected infection will be calculated as the minimum of a positive PCR sample collection date or the start date of an AE of COVID-19.

Time to COVID-19 infection will be calculated in days as (Date COVID-19 infection – Date of trial vaccination) + 1. Median time to COVID-19 infection within each cohort and vaccine arm (for Part A only), as well as for both cohorts combined, will be based on Kaplan-Meier estimates and corresponding 95% CIs based on the Brookmeyer-Crowley method. Along with the time to COVID-19 analyses, frequencies of subjects with COVID-19 infections will also be presented by visit. Time to COVID-19 infection plots will be created for each cohort and vaccination arm (for Part A only).

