11.14 Reporting

11.14.1 Reporting of SAEs and AESIs

All SAEs (collection starts at signing of ICF) and AESIs (collection starts upon vaccination) occurring throughout the entire course of the trial, to include the active trial and follow-up period, must be entered in the eCRF within 24 hours of awareness by the investigators, which triggers an autogenerated output to the drug safety department of ______, the contract research organization (CRO) for this trial.

In case the eCRF is unavailable, the SAE/AESI must be reported to **by** telephone or fax within 24 hours of becoming aware of the SAE and/or AESI as follows:

ABIVEO V2		
ABNCoV2-03	Edition 8.0	
SAE/AESI Hotline:		
• •		
SAE/AESI Hotline Fax:		
•		

The investigator should not delay reporting because of missing information. Nonetheless, the report should be as complete as possible. This initial report should include, at a minimum, sufficient information to permit identification of the following:

- The reporter (investigator's name and contact information)
- The subject
- Involved trial medication
- AE(s)
- Seriousness criterion
- Date of onset

is responsible for expedited reporting to the involved regulatory authorities according to applicable laws and guidelines, and for safety report distribution to participating investigators, IECs or IRBs and Human Research Protection Offices.

Regulatory authorities will be notified as soon as possible but no later than 7 days after date of first receipt of fatal or life-threatening SUSAR (Suspected Unexpected Serious Adverse Reaction) with an at least possible relationship to the IMP and no later than 15 days after knowledge of any non-fatal or non-life-threatening SUSAR.

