**Table 2: Details of Trial Design**

Design Element	Description
Study phase and study population	Phase 3, healthy adult subjects previously vaccinated for SARS-CoV-2
Design type	Part A: Parallel Part B: Single arm
Control Method	Part A: Active controlled, Comirnaty Part B: None
Blind level	Part A: Double blind Part B: Open label
Method of Assignment	Part A: Randomized 1:1 to a single dose of ABNCoV2 or Comirnaty, stratified by age group (<65 years vs. ≥65 years) and prior vaccination regimens, within each cohort. Part B: Non-randomized, all assigned to a single dose of ABNCoV2

Design Element	Description
Duration of Trial Participation	Screening: 2 Weeks Active Trial Phase: 4 Weeks Follow-up: 22 Weeks
Dose Adjustment Rules	Not applicable, single dose given on Day 1
Planned Interim Analyses	No interim analysis of immunogenicity is planned; however, a data monitoring committee will review cumulative safety data throughout the trial. No immunogenicity data will be reviewed prior to the primary analysis.
Timing of Primary Analysis	The primary analyses of immunogenicity and analyses of safety will be performed once all subjects within a trial part have completed the 8-week Follow-up 1 visit. Data will be cleaned through the 8-week timepoint. A data review meeting will be conducted to review the key trial data and determine if strategies to handle other intercurrent events are needed in addition to the strategies to handle the planned intercurrent events in a blinded manner. Treatment assignment will not be unblinded for the primary analyses until the data are locked and analysis populations and strategies to handle intercurrent events are set.
Timing of Subsequent Analyses	Follow-up analyses will be performed once all subjects have completed the 3 month and the 6 month follow-up visits, respectively. The final analysis for the trial will occur once all subjects have completed all follow-up or have withdrawn early from the trial and the database has been locked.

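### SAP 4.6.8 sets an end date for uninfected subjects but none for infections, which can bias the exploratory Kaplan-Meier infection curves upward before the final analysis

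*SAP*

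**What the plan says.** SAP 4.6.8 describes time to COVID-19 infection by trial part, cohort and (Part A) arm, "using the safety analysis set as an exploratory safety analysis".

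- **Events.** "PCR results and AE data will be used to determine the occurrence of COVID-19 infection for each subject". The infection date "will be calculated as the minimum of a positive PCR sample collection date or the start date of an AE of COVID-19". Neither date is tied to a visit, and no latest date is given.
- **Non-events.** Subjects without a positive result "will be censored at the date of the last visit attended prior to the analysis".
- **Summaries.** Medians from "Kaplan-Meier estimates and corresponding 95% CIs based on the Brookmeyer-Crowley method", infection frequencies by visit, and time-to-infection plots.

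Infections can enter the database between visits. Confirmed COVID-19 is an AESI (protocol 11.9.1), reportable even when detected outside the trial (11.11). PCR may be done at unscheduled visits (8.4). AESIs "must be entered in the eCRF within 24 hours of awareness by the investigators", in follow-up as well as in the active phase (11.14.1).

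On timing, SAP Table 2 and 4.7 trigger the primary analysis when every subject in a trial part has completed the 8-week call (FU1). Table 2 adds: "Follow-up analyses will be performed once all subjects have completed the 3 month and the 6 month follow-up visits, respectively". Protocol 12.10.2 instead places the 3- and 6-month data in one analysis at the end of the trial.

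**The concern.** Kaplan-Meier estimation needs a censoring time that does not depend on whether the subject is later infected. Under 4.6.8 as written it does depend on that. Past the last visit, an uninfected subject leaves the risk set although still under observation. A subject whose infection is reported before the next visit stays in until the infection date. Late event times are therefore divided by too few people at risk, and the error is always upward.

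The primary analysis, which goes into the full CSR, is exposed because early enrollees are then at varying points beyond FU1. The output is a set of by-arm infection curves against an authorised vaccine. A steep late rise produced by the rule could be misread as waning protection.

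**Working it through.** The documents give no event count, rate or median for this analysis, so there is no figure of the plan's to reproduce.

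**1. Mechanism.** The estimator is S(t) = product over event times of (1 − d/n), where d is infections and n is subjects at risk. Suppose FU2 (days 91–105) is the last visit of every uninfected subject in an arm, and one infection dated day 120 is in the database. At day 120, n = 1 and d = 1, so the factor is 1 − 1/1 = 0. The curve drops to zero and a median of 120 days is reported, whatever the true risk.

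**2. Who is between visits.** FU1 is day 56–70, FU2 day 91–105 and FU3 day 182–196. The gap from FU2 to FU3 is 182 − 105 = 77 to 196 − 91 = 105 days. Assume lock 14 days after the last subject's FU1. The last enrollee then has 56 + 14 = 70 to 70 + 14 = 84 days of follow-up, and the first enrollee has that plus the accrual span:

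- 60 days: 130–144. Nobody has reached FU3.
- 120 days: 190–204. Only the earliest have.
- 240 days: 310–324. Many have.

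**3. Simulation inputs.**
- From the documents: the visit windows, and about 250 per arm (500 per Part A cohort, 1:1).
- Assumed: constant hazard; true risk 10.0% at day 182 (hence 1 − 0.9^(98/182) = 5.5% at day 98 and 1 − 0.9^(150/182) = 8.3% at day 150); accrual of 60, 120 or 240 days; 25%, 50% or 100% of infections after the last visit in the database at lock.
- 300 runs per setting, so the means carry some Monte Carlo error.

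**4. Mean estimated cumulative infection, rule as written.**

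| Analysis | Accrual | Day (true) | 25% / 50% / 100% reported | Curve falls to zero |
|---|---|---|---|---|
| Primary | 240 d | 182 (10.0%) | 10.4 / 10.9 / 11.7% | none |
| Primary | 120 d | 182 (10.0%) | 12.8 / 16.9 / 22.9% | none |
| Primary | 60 d | 150 (8.3%) | 33.6 / 57.5 / 78.7% | 29 / 54 / 77% of runs |
| 3-month, if run | 240 d | 182 (10.0%) | 10.3 / 10.3 / 11.2% | none |
| 3-month, if run | 120 d | 182 (10.0%) | 11.1 / 12.1 / 13.8% | none |
| 3-month, if run | 60 d | – | – | 77 / 95 / 100% of runs |
| Final | all three | 182 (10.0%) | 9.9–10.2% | none |

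Up to about day 98 the bias is at most about 0.6 points in every 10%-risk setting. With no between-visit reporting there is no upward bias.

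Few events are needed. In the 3-month, 120-day, 50% setting, on average 2.2 post-visit infections per arm, out of 21.0 in all, give 12.1%, against 10.1% under aligned end dates.

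**5. Other risk levels (primary analysis, 50% reported, day 182).** A true 5% gives 9.3% (120-day accrual) and 5.4% (240-day). A true 20% gives 32.0% and 21.4%, and at 120 days the curve falls to zero in 1% of runs.

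**6. One end date for both.** Counting only infections dated on or before the last visit attended, the primary-analysis estimate at day 182 is 9.4–9.8% (120-day) and 9.9–10.1% (240-day). With 60-day accrual the curve simply ends near day 105 at about 5.9%. No collapse can occur.

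**The case against.** **The SAP never says that infections after the last visit are counted.** This is correct: it is inferred from the absence of a limit. SAP Table 2 limits data cleaning for the primary analysis to week 8, and the PCR summary in 4.5.6.1 bounds positives by visit, so the authors may have visit-bounded data in mind. But a cleaning horizon is not a data cut, and 4.6.8 censors at whichever visit was last attended, which for early enrollees can be FU2 or FU3. Cutting events alone at week 8 would reverse the error: the curve would stay flat at about 1 − 0.9^(63/182) = 3.6% against a true 10.0% at day 182. Only a common end date is harmless, and 4.6.8 does not state one.

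**The size is uncertain and may be small.** This stands. The 24-hour rule runs from investigator awareness. Subjects are also asked about infection at visits, and infections learned of that way precede the visit and cause no bias. The only accrual evidence is that enrolment was extended (SAP 2.1), which favours the lower figures. Because the lock is per trial part, slow Cohort 1 accrual also moves Cohort 2 towards FU3. With 2% infection per 30 days and Cohort 2 enrolled over 90 days, a 180-day Part A span gives 12.2 / 12.9 / 13.7% in Cohort 2 at day 185 for 25 / 50 / 100% reporting, against a true 11.7%. A 270-day span gives 11.7–11.8%. These spans are assumptions too.

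**Collapse of the curve.** A reader might infer that the curves will collapse. The documents do not support that: it needs short accrual, with almost nobody yet at FU3.

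**Two of three planned analyses.** A reader might also infer that two of the three planned analyses are biased. The separate 3-month analysis appears in SAP Table 2 but not in protocol 12.10.2, and neither document says 4.6.8 is repeated then.

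**Consequence.** The analysis is exploratory, has no test, and applies the same rule to both randomised arms. The only Kaplan-Meier number specified is the median, which at these risks is not reached unless the curve collapses. What remains exposed is the late part of the plots.

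**Conclusion.** The point holds in a limited form. Followed literally, SAP 4.6.8 makes censoring depend on outcome and can only push estimated infection upward. It does so mainly after about Week 13, at the primary analysis and at any 3-month run. The final analysis is essentially unaffected, and the primary and key secondary tests do not use this analysis.

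At an assumed 10.0% risk by day 182, the overstatement at the primary analysis is 0.4 to 1.7 points with 240-day accrual and 2.8 to 12.9 points with 120-day accrual, for 25% to 100% between-visit reporting. Among the spans simulated at this risk, collapse occurred only at 60 days. The figures rest on an assumed constant hazard, accrual span, reporting share and lock date. With no between-visit reporting, or with later records cut at the visit, the bias disappears. Severity: minor.

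**What to change.** In SAP 4.6.8, state one end date for events and censoring: the subject's last completed scheduled contact in that analysis.

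- Count an infection only if dated on or before that contact. Otherwise censor the subject there and carry the infection to the next analysis.
- Say that the FU1 call counts as a contact and that symptom-triggered unscheduled visits do not extend the end date. Such a visit tends to occur because of the infection, so letting it extend follow-up would bring the imbalance back.
- Show numbers at risk under each curve.
- Say at which analyses 4.6.8 is run, and reconcile SAP Table 2 with protocol 12.10.2 on the 3-month analysis.

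The cost is a few sentences and a small programming change. A few late infections are left out of the early analysis and appear in the next one. Truncating everyone at the visit that defines the analysis is also valid, but it is not equivalent: at the primary analysis it discards FU2 and FU3 follow-up already available from early enrollees.

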#### **4.6.9. Thrombocytopenia**

An exploratory safety analysis of thrombocytopenia will be performed for the active trial phase. To explore prevalence at baseline, both Medical History and Baseline Signs and Symptoms will be reviewed for pre-existing cases. Events will be queried based on the MedDRA high level term of “Thrombocytopenias” and the MedDRA preferred term of “Platelet count decreased”.

Post vaccination AE data will also be reviewed for incidences of thrombocytopenia using the same MedDRA high level term of “Thrombocytopenias” and the MedDRA preferred term of “Platelet count decreased”.

A summary of changes from baseline in platelet counts to the worst post-vaccination value (based on the lowest post-vaccination platelet count) will also be analyzed by trial part, cohort,

and vaccination arm (Part A only). Continuous summary statistics will be provided for both the actual values at baseline and worst value post-vaccination, as well as for the change from baseline to worst post-vaccination value. A histogram of the changes from baseline for the combined cohorts will be created with groupings for vaccination arm in Part A, and overall for Part B.

#### **4.6.10. Hyperkalaemia**

An exploratory safety analysis of hyperkalemia will be performed for the active trial phase in a similar fashion to thrombocytopenia. To explore prevalence at baseline, both Medical History and Baseline Signs and Symptoms will be reviewed for pre-existing cases. Events will be queried based on the MedDRA preferred terms of “Hyperkalaemia” and “Blood potassium increased”.

Post-vaccination AE data will also be reviewed for incidences of hyperkalaemia using the same MedDRA preferred terms of “Hyperkalaemia” and “Blood potassium increased”.

A summary of changes from baseline in potassium levels to the worst post-vaccination value (based on the highest post-vaccination potassium level) will also be analyzed by trial part, cohort, and vaccination arm (Part A only). Continuous summary statistics will be provided for both the actual values at baseline and worst value post-vaccination, as well as for the change from baseline to worst post-vaccination value. A histogram of the changes from baseline for the combined cohorts will be created with groupings for vaccination arm in Part A, and overall for Part B.

#### **4.7. Interim Analysis**

The primary analysis for the trial will occur after subjects have completed the 2 months of follow-up within a trial part. A data review meeting will take place to review any potential exclusions from the Immunogenicity Analysis Set. Once the trial data are clean and any queries resulting from the data review meeting are resolved, the database will be locked and unblinded for the analysis. Planned immunogenicity and safety analyses will be performed once the lock has occurred and the immunogenicity results are available. A full CSR will be written for this analysis.

#### **4.8. Changes to Protocol-planned Analyses**

##### Nucleocapsid Protein IgG Testing

A change from the protocol on the use of the nucleocapsid antibody testing to define intercurrent events for the primary estimand has been incorporated into this SAP. The intercurrent event of COVID-19 infection, and use of the “while on treatment” strategy, is only intended to exclude the significant effects an infection would have on the immunogenicity response for a subject. The antibody response to the trial vaccine could not be distinguished from the antibody response to a SARS-CoV-2 infection in this situation. As no current vaccines contain the nucleocapsid protein, the nucleocapsid IgG test was added to ensure subjects with recent infections were not included in the analyses.

Nucleocapsid protein IgG testing results in a study of the kinetics of these antibodies after SARS-CoV-2 infection show the average peak occurred 72 days after a positive PCR test result,

and a 90.8% sensitivity in samples collected >14 days after the start of symptoms (Loesche, 2022). This suggests that subjects who had SARS-CoV-2 infection prior to baseline may continue to have increases in antibody levels against the nucleocapsid protein during the 2-week period from baseline to the primary endpoint time point. On the other hand, subjects who had new infection after baseline may not have significant increases during the short period of time. Thus, the nucleocapsid protein antibody results are not a good indicator for natural infection acquired between baseline and Week 2.

The risk of missing natural COVID-19 infections by not accounting for nucleocapsid IgG test results is low. Subjects are required to test negative for COVID-19 at screening via PCR test. Additionally, those attending the Week 1 or Week 2 visits with clinically relevant symptoms are tested by PCR for infection, such that concurrent infections during the 2 week period should be captured either by PCR test or adverse event reporting.

The risk of excluding subjects who had older infections that may have occurred prior to baseline is not negligible due to the kinetics of the nucleoprotein protein IgG test. Therefore, in the interest of having a more inclusive primary analysis it has been decided to remove the nucleocapsid protein IgG testing from the intercurrent event of COVID-19 infection and retain the results for a sensitivity analysis.

